9.2.1. Hematology

The following laboratory tests will be included: hemoglobin, hematocrit, leukocytes, differential leukocytes (absolute values and as a percentage of total leukocytes), erythrocytes, thrombocytes and activated partial thromboplastin time. All hematology data by patient will be presented in a listing.

9.2.2. Clinical Chemistry

The following laboratory tests will be included: arterial pH, CRP, urea, creatinine, creatine phosphokinase, total protein, albumin, glucose, sodium, potassium, chloride, bicarbonate, and lactate. All chemistry data by patient will be presented in a listing.

The following normal range will be used for arterial pH: 7.35 – 7.45

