#### **6.2.4 Safety Assessments**

The following assessments will be considered safety measurements:

- Vital signs, including blood pressure, heart rate, oxygen saturation, respiratory rate, and body temperature at baseline and at all visits from Day 1 to Day 28. During the 3 dosing days (Day 1 to Day 3), repeated vital sign measurements will be performed (see Section 6.3.4).
- Physical examination at baseline and at all visits from Day 1 to Day 28
- 12-lead ECG at baseline and at visits on Days 3 and 14
- Local laboratory at baseline and at visits on Days 1, 3, 5, 7, 14, 21, and 28:
  - Hematology
  - Clinical chemistry, including liver function parameters (aspartate aminotransferase [AST], alanine aminotransferase [ALT], gamma-glutamyl transpeptidase [GGT] lactate dehydrogenase [LDH], and bilirubin; excluding AP)
- Serology (IgG, IgE and total immunoglobulin) at baseline and at visits on Days 14 and 28
- Anti-drug antibodies at baseline and at visits on Days 14, 28, 60, and 90. Samples taken on Days 60 and 90 will only be analyzed in case of a positive result on Day 28
- Concomitant medication at screening, baseline, and all visits from Day 1 to Day 28
- AEs during the duration of the study (see Section 6.3.14)
- Mortality (monitored continuously throughout the study)

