### **6.3.7 Laboratory Tests Performed by the Local Laboratory**

Blood samples will be collected for local laboratory measurements at baseline, and at visits on Days 1, 3, 5, 7, 14, 21, and 28 (see Section 13.1 [Table 13-1] and Section 13.2 [Figure 13-1]). Approximately 178 to 208 mL (35 to 42 teaspoons) of blood will be collected per patient in total during the study, including tests performed in the local and in the central laboratories.

To decide when to stop RRT (see Section 6.3.9), local urine creatinine, urine volume, and serum creatinine samples will be taken and the creatinine clearance calculated. This will be based on local laboratory results.

The following laboratory tests should be performed at the visits indicated above, unless otherwise indicated:

**Clinical chemistry:** CRP, ALT, AST, GGT, urea, LDH, creatinine, bilirubin, creatine phosphokinase, total protein, albumin, glucose, sodium, potassium, chloride, bicarbonate, and lactate.

Note: AP is not allowed to be measured locally until Day 14 (see Section 6.3.8.2).

**Hematology:** hemoglobin, hematocrit, leukocytes, differential leukocytes, erythrocytes, thrombocytes, activated partial thromboplastin time.

**Pregnancy test:** only at baseline. Blood human chorionic gonadotropin (hCG) or urine hCG (dipstick). See Section 6.4 for additional details.

When the diagnosis of AKI was made according to one of the AKIN serum creatinine criteria (absolute or relative increase, see inclusion criteria 5a and 5b), the confirmative fluid-corrected serum creatinine sample with results available prior to randomization and prior to study drug administration is to confirm continuation of AKI.

Note that platelets, bilirubin, creatinine, and urine output are required to obtain a SOFA score.

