## 10.1 Monitoring

### 10.1.1 External Data Monitoring Committee

An independent DMC will review the results of the interim analysis and select the optimum recAP dose for Part 2 of the study (see Section 7.7.5). The DMC will conduct three additional reviews of the safety data by teleconference once the first 7 days of laboratory data are available for the following: 75 patients in Part 1, 60 patients in Part 2, and 125 patients in Part 2. In each case, the milestone will be patients with at least 7 days of laboratory data. Additional electronic reviews will be conducted of unblinded AE listings after 25, 50 and 100 patients in Part 1 and 30 and 90 patients in Part 2. The DMC can also request ad hoc

reviews. Accumulating safety and efficacy data will be reviewed at predefined milestones during Part 1 and Part 2 of the study by the independent DMC as described in the DMC charter as follows:

- Electronic Review 25 subjects
- Electronic Review 50 subjects
- Teleconference 75 subjects
- Electronic Review 100 subjects
- Face to Face Meeting-interim analysis-120 subjects
- Ad hoc Review- (if needed) between 90-120 additional subjects
- Teleconference 60 additional subjects from Part 2 (at least 180 total)
- Electronic Review 90 additional subjects from Part 2 (at least 210 total)
- Teleconference 125 additional subjects from Part 2 (at least 245 total)
- Ad hoc Review- (if needed) between 125-170 subjects from Part 2 (at least 245-290 total).

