8.2.2.2. Other Organs

Liver Enzymes

Liver enzymes is assessed by AST (U/L), ALT (U/L), GGT (U/L), LDH (U/L) and bilirubin ($\mu\text{mol/L}$) at Baseline, Day 1, Day 3, Day 5, Day 7, Day 14, Day 21 and Day 28.

The observed values and change from baseline for liver enzymes will be calculated by visit and summarized by descriptive statistics.

Time-course plots similar to the plot being produced for the primary endpoint will be presented for mean AST, ALT and LDH displaying the optimal recAP and placebo groups only.

All liver enzymes data will be listed.

Lung Function

Lung function is assessed, for patients on mechanical ventilation, by PaO₂, P/F ratio, PEEP (cmH₂O) and tidal volume (mL/kg) daily from Day 1 to Day 28. The observed values and change from baseline for PaO₂, P/F ratio, PEEP and tidal volume will be calculated by visit and summarized with descriptive statistics. For non-mechanical ventilation liters of administered oxygen will be assessed.

Table 8-2 Normal Ranges for Lung Function Parameters

Parameter	Normal Range
PCO ₂	4.7 – 6.4 kPa or 35-48 mmHg
PO ₂	10.0 – 13.3 kPa or 75 – 100 mmHg
Oxygen saturation	95 – 100%

The following conversion rate will be performed for PO₂ and PCO₂ where needed
 kilopascal (kPa) x 7.5 = mmHg

All lung function data will be listed.

Mechanical Ventilation from Day 1 to Day 28

A ventilator-free day is defined as a day on which a patient was not on ventilator (invasive or non-invasive mechanical ventilation). The start and stop dates of the patient been under mechanical ventilation is collected in the eCRF, therefore days not on ventilator correspond to days that are outside of the start and stop dates of when the patient is on mechanical ventilation. If the method of mechanical ventilation is changed with no interruption, it corresponds to the same episode of mechanical ventilation.

Should a patient die or withdraw prior to Day 28, the days remaining in this period will be counted as per the status of the patient at time of death or withdrawal.

Ventilator-free days are calculated as 28 days minus the number of days a patient is on ventilator during this period. Descriptive statistics will be presented for the number of ventilator-free days.

Time to being off ventilator from Day 1 to Day 28, for those patients that are on ventilator at Day 1, will be compared between treatment groups by displaying Kaplan-Meier plots. Time to being off ventilator is calculated as:

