9.2. Laboratory Evaluations

Laboratory assessments not used for the efficacy analysis will be used for the safety analysis and be performed by the local laboratory. All summaries will be based on the units provided defined in the eCRF, no conversion will be done. Also, the out of normal range data will be presented.

Hematology and clinical chemistry assessments will be summarized according to the visits and will be assessed at Baseline, Day 1, 3, 5, 7, 14, 21 and 28. Shift tables presenting baseline and post-baseline values below, within, above or below the normal range (normal ranges as provided by the local laboratories), and count tables at each visit will be presented for hematology and clinical chemistry tests with numeric values below, within or above the normal range (normal ranges as provided by the local laboratories) by treatment group for patients in the Safety Set. The percentage will be based on the number of patients who have attended the visit.

Only scheduled assessments will be included in the laboratory summaries. In case of repeat values the last assessment will be used for pre-dose visits and the first value for post-dose visits.

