milestone will be patients with at least 7 days of laboratory data or who were randomized but discontinued or died prior to completing 7 days. The following outputs will be produced for these safety reviews:

Table 14.1.1.1.1	Disposition at Interim Analysis All Enrolled Set
Table 14.1.1.6.1	Concomitant Medications at Interim Analysis Safety Set
Table 14.3.1.1.1	Treatment Emergent Adverse Events at Interim Analysis by System Organ Class and Preferred Term Safety Set
Table 14.3.1.1.2*	Serious Treatment Emergent Adverse Events at Interim Analysis by System Organ Class and Preferred Term Safety Set
Table 14.3.1.3.1	Treatment Emergent Adverse Events at Interim Analysis by Relationship to Study Drug Safety Set
Table 14.3.2.1*	Summary of Cause of Death at Interim Analysis by System Organ Class and Preferred Term Safety Set
Table 14.3.5.3.1	Hematology Shift Table by Treatment at Interim Analysis Safety Set
Table 14.3.5.3.2	Laboratory Results: Hematology at Interim Analysis Safety Set
Table 14.3.5.4.1	Clinical Chemistry Shift Table by Treatment at Interim Analysis Safety Set
Table 14.3.5.4.2	Laboratory Results: Clinical Chemistry at Interim Analysis Safety Set
Table 14.3.6.2.1	Change from Baseline in Vital Signs at Interim Analysis Safety Set
Figure 14.3.6.2.1	Time-course plot of Vital Signs at Interim Analysis Safety Set
Table 14.3.7.1.1*	APACHE II Score at Interim Analysis Safety Set
Listing 16.3.1.1.2*	Deaths Safety Set

* Outputs were requested after the first DMC meeting.

References to ‘Interim Analysis’ will be removed from all titles and footnotes when outputs are provided at safety reviews.

Additional electronic reviews of AE listings provided by pharmacovigilance (PVG) will be conducted at planned time points and the DMC can request ad hoc reviews. See [Table 15-2](#) for a full summary of the planned reviews.

12. Changes in the Planned Analysis

As part of the primary efficacy analysis an additional analysis set PP Day 1-7 Part 1 has been added. The protocol states that primary endpoint should be carried out separately for Part 1 and Part 2, however to do this analysis on the PP Set, the PP Day 1-7 Part 1 Set is needed to be defined to obtain the analysis for Part 1 of the study.

The following are changes from the Protocol Amendment v2.0:

Table 12-1 Summary of Changes from Planned Analysis and Reason

Change	Change
List of subgroups (Sections 2.3 and 8)	Microbial Infection added

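### Five liver tests that the protocol classes as safety measurements are left out of the SAP's Safety Set chemistry tables

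*SAP*

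**What the plan says.** Protocol 6.2.4 lists among the safety measurements "Clinical chemistry, including liver function parameters (aspartate aminotransferase [AST], alanine aminotransferase [ALT], gamma-glutamyl transpeptidase [GGT] lactate dehydrogenase [LDH], and bilirubin; excluding AP". Protocol 6.3.7 gives the local chemistry panel as "CRP, ALT, AST, GGT, urea, LDH, creatinine, bilirubin, creatine phosphokinase, total protein, albumin, glucose, sodium, potassium, chloride, bicarbonate, and lactate".

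SAP 9.2 divides the laboratory data: "Laboratory assessments not used for the efficacy analysis will be used for the safety analysis and be performed by the local laboratory". It then specifies, on the Safety Set, shift tables and counts below, within and above the normal range. SAP 9.2.2 lists the chemistry tests covered: "arterial pH, CRP, urea, creatinine, creatine phosphokinase, total protein, albumin, glucose, sodium, potassium, chloride, bicarbonate, and lactate".

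The liver tests appear in SAP 8.2.2.2: "The observed values and change from baseline for liver enzymes will be calculated by visit and summarized by descriptive statistics". That section adds time-course plots for AST, ALT and LDH and a listing. Under SAP 8.2.2 these summaries use the ITT Combined Set. SAP 4.3.2 analyses that set by randomised arm and excludes patients recruited during the interim analysis to doses not taken into Part 2.

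SAP Section 4 says that those patients' safety data will be analysed, and that safety summaries include patients recruited at any point.

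For the DMC, SAP Section 11 names two chemistry outputs in each package, Tables 14.3.5.4.1 ("Clinical Chemistry Shift Table by Treatment at Interim Analysis Safety Set") and 14.3.5.4.2. It names no output from 8.2.2.2.

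**The concern.** The protocol treats the five tests as safety data. The SAP gives them the outputs and the analysis set of an efficacy endpoint. The usual displays for finding individual patients with abnormal liver tests are shifts from normal to high and counts above range, by treatment received. These are specified for the rest of the panel but not for the liver tests.

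The gap matters somewhat more here because Protocol 5.6 withholds alkaline phosphatase results to Day 14, as the study drug raises that enzyme and would mislead on liver function. The five tests are therefore the main laboratory view of the liver in the period when drug exposure is highest.

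The efficacy label also brings in the exclusion of interim-period patients on the dropped doses. SAP Section 4 says that safety data will not be subject to that exclusion.

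**Working it through.** **1. Which tests are missing.** The Protocol 6.3.7 panel has 17 tests and the SAP 9.2.2 list has 13.
- In the protocol panel but not in SAP 9.2.2: ALT, AST, GGT, LDH and bilirubin, exactly five.
- In SAP 9.2.2 but not in the protocol panel: arterial pH.
- Check: 17 − 5 + 1 = 13.

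**2. Is the split applied evenly?** No. CRP, creatinine and urea/BUN are summarised under efficacy (SAP 8.2.2.1 and 8.2.2.3) and also stay in SAP 9.2.2. An efficacy role does not by itself keep an analyte out of the safety tables.

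**3. What each group of tests receives.**

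| Output | Tests in SAP 9.2.2 | Five liver tests (SAP 8.2.2.2) |
|---|---|---|
| Analysis set | Safety Set | ITT Combined Set |
| Grouping | treatment received | randomised arm |
| Shift tables | yes | none specified |
| Out-of-range counts | yes | none specified |
| Descriptive statistics by visit | not described in 9.2 | yes, including minimum and maximum |
| Plots | none specified | AST, ALT and LDH |
| Listing | yes | yes |

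**4. Planned size.** 4 × 30 + 2 × 85 = 290, which reproduces the total in SAP 4.1.

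**5. Patients outside the liver summaries under SAP 4.3.2.** Protocol 3.1 estimates 50 patients recruited during the interim, allocated 1:1:1:1. Two of the four arms are then dropped.
- Expected number: 50 × 2/4 = 25, or 12.5 per dropped dose.
- With 40 recruits: 40 × 2/4 = 20. With 60 recruits: 60 × 2/4 = 30.
- Chance range at 50 recruits: 18 to 32 (95%, treating allocation as simple binomial with probability 0.5).

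**6. As a share.** Interim-period patients on placebo or the selected dose count towards Part 2, so only the 25 are added to the planned total.
- All patients: 25 / (290 + 25) = 25/315 = 8%.
- Patients on recAP: 25 / (3 × 30 + 85 + 25) = 25/200 = 12.5%.
- Patients on the two dropped doses: 25 / (2 × 30 + 25) = 25/85 = 29%.

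Steps 5 and 6 assume that every randomised patient is dosed.

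**7. Text that conflicts with the exclusion.** SAP 8.2.2 uses the ITT Combined Set but also says that the summaries include all patients randomised in Part 1 or Part 2. SAP Table 12-1 says that the secondary summaries cover all patients, as in the safety analysis. SAP Section 4 and SAP 4.3.2 exclude the interim-period patients on dropped doses. The same tension affects listings: Section 4 includes everyone, whereas 8.2.2 bases listings on the ITT Combined Set.

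**The case against.** **The split did not start with the SAP.** Protocol 7.3.2 already makes the five tests a secondary endpoint. Protocol 7.3.4 and 7.7.3 use wording that confines safety laboratory data to parameters outside the efficacy analysis, although that wording may qualify only urinalysis. This stands as to origin. It does not undo Protocol 6.2.4, and the two roles are compatible.

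**The duplicated tests are not an exact precedent.** The efficacy values of CRP, creatinine and BUN come mainly from the central laboratory and the safety values from the local one, whereas the liver tests are local only. This also stands. It may explain the list, but it gives no reason to leave the local liver results out of the local chemistry tables.

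**The data are not lost.** SAP Section 4 includes quartiles, minimum and maximum in descriptive statistics, so a large rise at a scheduled visit would appear as that arm's maximum. Values are listed, the liver component of SOFA is summarised by visit, and Protocol 6.5 requires clinically significant abnormalities to be recorded as adverse events. A reader might infer that large rises would be hidden in arm means; the SAP does not support that. What is missing is the number of patients affected and their movement from baseline category.

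**The DMC content is unknown.** A reader might infer that the dose was selected without liver tests by arm. The documents do not show this. The chemistry tables in SAP Section 11 are named without analytes, the protocol's own chemistry panel includes the five tests, and the shells, DMC charter and interim analysis plan are not available. The DMC also received adverse event tables, could request ad hoc reviews, and had outputs added after its first meeting. SAP 8.1.4 describes the interim in the past tense, so no change to this SAP can affect dose selection.

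**Conclusion.** The point holds for the final safety tables. Five of the 17 protocol chemistry tests, all named as safety measurements, have no shift table, no out-of-range count and no summary by treatment received. This follows from the SAP text without further assumption.

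The population point is conditional. On the explicit ITT Combined definition, about 25 patients are outside the liver summaries. That figure rests on the estimate of 50 interim-period recruits, equal allocation and all patients being dosed. SAP 8.2.2 and Table 12-1 can be read as including them, so the defect is an unresolved conflict. It would be too strong to say that these patients have no liver data, because SAP Section 4 puts every patient in the listings.

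The DMC point is also conditional. If Tables 14.3.5.4.1 and 14.3.5.4.2 follow the SAP 9.2.2 list, the DMC packages lack liver tests by arm.

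This should be fixed, but it does not affect the primary analysis, type I error or power.

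**What to change.** 1. In SAP 9.2.2, add AST, ALT, GGT, LDH and bilirubin to the chemistry tests, on the Safety Set by treatment received, with the shift and out-of-range tables already specified in SAP 9.2. Adjust the splitting sentence in 9.2 so that an efficacy role does not exclude a test from the safety tables.
2. Keep the SAP 8.2.2.2 summaries and plots unchanged.
3. In SAP Section 11, state that the chemistry tables for any remaining DMC review include the five tests.
4. Reconcile SAP 8.2.2 and Table 12-1 with SAP Section 4 and SAP 4.3.2, for summaries and for listings, so that it is clear whether interim-period patients on the dropped doses are included.

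The data are already collected and the table formats already specified. With step 1, the expected number of patients in the liver safety tables rises from 290 to about 315, and each dropped-dose arm from 30 to about 42.5 (30 + 12.5), if all are dosed. The cost is SAP wording and slightly longer tables.

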9.2.3. Urinalysis

No urinalysis will be performed as part of the safety analysis, all urinalysis parameters will be analyzed as part of the efficacy analysis (see [Section 8.2.2.3](#)).

9.2.4. Pregnancy

Either a blood human chorionic gonadotropin (hCG) or urine hCG (dipstick) pregnancy test will be performed for all females of childbearing potential at baseline. All pregnancy data by patient will be presented in a listing.

9.3. Vital Sign Measurements

Vital signs are assessed at Baseline, Day 1, 2, 3, 4, 5, 6, 7, 14, 21 and 28, where systolic blood pressure (mmHg), diastolic blood pressure (mmHg), temperature (°C), heart rate (beats/minute), oxygen saturation (%) and respiratory rate (breaths/minute) are recorded.

For Day 1, 2 and 3, vital signs excluding temperature are assessed immediately prior to the start of infusion of study drug, 5 minutes after start of infusion, 30 minutes after start of infusion, immediately after the completion of the study drug infusion, 30 and 60 minutes after completion of infusion. On day 1 only, vital signs will additionally be assessed 2 hours, 3 hours, 4 hours and 5 hours after completion of study drug infusion.

Summary tables presenting observed values and changes from pre-dose will be presented for vital sign data at pre-dose, 5 minutes after start of infusion, 30 minutes after start of infusion, immediately post-dose and 30 and 60 minutes post-dose, 2 hours post-dose, 3 hours post-dose, 4 hours post-dose, 5 hours post-dose for Day 1, at pre-dose, 5 minutes after start of infusion, 30 minutes after start of infusion, and 30 and 60 minutes post-dose for Day 2 and 3 by treatment group for patients in the Safety Set.

Summary tables presenting observed values and changes from baseline will be presented for vital sign data at Baseline, Day 1, 2, 3, 4, 5, 6, 7, 14, 21 and 28 by treatment group for patients in the Safety Set. Additionally, counts and percentages of patients with temperature <36°C, ≥36 °C to ≤38°C and >38°C will be presented by treatment group for each timepoint at which temperature is assessed.

A time-course plot of vital signs at the interim analysis with associated standard error bars for each timepoint will be presented for all three recAP doses and placebo groups.

All vital sign data by patient will be presented in a listing.

9.4. Physical Examination

Physical examination is assessed at baseline and at all subsequent visits up to the Day 28 visit. Each visit captures the status of a body system and any finding associated with the body system as normal, abnormal, or not done. The following body systems are captured: heart, lungs, head, neck, abdominal, neurological-non-MS (i.e., neurological findings not related to multiple sclerosis) skin, extremities and others (if applicable). Physical examination results for all patients will be presented in a listing.

9.5. Electrocardiogram

All patients will have a 12-lead ECG performed at baseline, Day 3, and Day 14.

Summary tables presenting observed values and changes from baseline will be presented for ventricular rate (bpm), PR Interval (msec), QRS Duration (msec), QT Interval (msec), QTcB Interval (msec), by treatment group for patients in the Safety Set. Changes from baseline to each scheduled post-baseline visit will be presented.

The ECG interpretations will be summarized in shift tables comparing the ECG values of each post-baseline visit with the value at the baseline visit for the Safety Set. The percentage will be based on the number of patients who have attended the visit. In addition the worst post-baseline ECG value will be compared with the value at the baseline visit (with worst of all being Abnormal and best being Normal).

Electrocardiogram data for all patients will be presented in a listing.

10. Pharmacokinetics and Pharmacodynamics

The pharmacokinetics and pharmacodynamics analyses will be described in the Population Pharmacokinetics/ Pharmacodynamics Report Analysis Plan.

11. Interim Analysis

An unblinded interim analysis will be conducted on the Part 1 data to determine the optimal recAP dose for Part 2. This analysis will compare the 4 treatment groups from Part 1 on the primary efficacy endpoint, and a selection of the safety data. The interim analysis will be conducted when the first 7 days of laboratory data have been collected for 120 patients from Part 1, unless the patient was randomized but died or discontinued prior to completing 7 days.

To maintain the blind, the interim analysis will be conducted and delivered by an unblinded PPD Biostatistics team located at a different site to the blinded PPD biostatistics personnel involved in the study. The results will be reviewed by an independent DMC, who will make the dose selection decision. A futility analysis will also be conducted at the interim analysis. If none of the 3 recAP doses in Part 1 show evidence of efficacy (i.e., all 3 groups have 1-sided, unadjusted p-value greater than 0.8), then the study will be terminated.

The following outputs will be produced for the Interim Analysis:

Table 14.1.1.1.1	Disposition at Interim Analysis All Enrolled Set
Table 14.1.1.6.1	Concomitant Medications at Interim Analysis Safety Set
Table 14.2.1.1.1	Summary of Time-Corrected Endogenous Creatinine Clearance at Interim Analysis ITT Combined Set
Table 14.2.1.1.2	Sensitivity Analysis: Summary of Time-Corrected Endogenous Creatinine Clearance at Interim Analysis – Excluding Patients Who Died Prior to Day 8 ITT Combined Set
Table 14.2.1.2.1	ANOVA for Area Under the Time-Corrected Endogenous Creatinine Clearance Curve from Day 1 to Day 7 (AUC 1-7) at Interim Analysis ITT Combined Set
Table 14.2.1.2.2	Sensitivity Analysis: ANOVA for Area Under the Time-Corrected Endogenous Creatinine Clearance Curve from Day 1 to Day 7 (AUC 1-7) at Interim Analysis – Excluding Patients Who Died Prior to Day 8 ITT Combined Set
Table 14.2.1.2.3	SAS Output for the Primary Efficacy Endpoint at Interim Analysis: ANOVA for Area Under the Time-Corrected Endogenous Creatinine Clearance Curve from Day 1 to Day 7 (AUC 1-7) ITT Combined Set
Table 14.2.2.13	Analysis of Incidence of RRT from Day 1 to Day 7 at Interim Analysis ITT Combined Set
Table 14.2.9.1	Emax – Model Parameters Estimates at Interim Analysis ITT Combined Set
Table 14.3.1.1.1	Treatment Emergent Adverse Events at Interim Analysis by System Organ Class and Preferred Term Safety Set
Table 14.3.1.1.2	Serious Treatment Emergent Adverse Events at Interim Analysis by System Organ Class and Preferred Term Safety Set
Table 14.3.1.3.1	Treatment Emergent Adverse Events at Interim Analysis by Relationship to Study Drug Safety Set
Table 14.3.2.1	Summary of Cause of Death at Interim Analysis by System Organ Class and Preferred Term Safety Set
Table 14.3.5.3.1	Hematology Shift Table by Treatment at Interim Analysis Safety Set
Table 14.3.5.3.2	Laboratory Results: Hematology at Interim Analysis Safety Set
Table 14.3.5.4.1	Clinical Chemistry Shift Table by Treatment at Interim Analysis Safety Set
Table 14.3.5.4.2	Laboratory Results: Clinical Chemistry at Interim Analysis Safety Set
Table 14.3.6.2.1	Change from Baseline in Vital Signs at Interim Analysis Safety Set
Table 14.3.7.1.1	APACHE II Score at Interim Analysis Safety Set
Figure 14.2.9.1	Emax – Model Fitting at Interim Analysis ITT Combined Set
Figure 14.3.6.2.1	Time-course plot of Vital Signs at Interim Analysis Safety Set
Listing 16.3.1.1.2	Deaths Safety Set

The DMC will conduct three additional reviews of the safety data by teleconference once the first 7 days of laboratory data are available for: 75 patients in Part 1; 60 patients in Part 2 (total of 180 patients); and 125 patients in Part 2 (total of 245 patients). In each case the

milestone will be patients with at least 7 days of laboratory data or who were randomized but discontinued or died prior to completing 7 days. The following outputs will be produced for these safety reviews:

Table 14.1.1.1.1	Disposition at Interim Analysis All Enrolled Set
Table 14.1.1.6.1	Concomitant Medications at Interim Analysis Safety Set
Table 14.3.1.1.1	Treatment Emergent Adverse Events at Interim Analysis by System Organ Class and Preferred Term Safety Set
Table 14.3.1.1.2*	Serious Treatment Emergent Adverse Events at Interim Analysis by System Organ Class and Preferred Term Safety Set
Table 14.3.1.3.1	Treatment Emergent Adverse Events at Interim Analysis by Relationship to Study Drug Safety Set
Table 14.3.2.1*	Summary of Cause of Death at Interim Analysis by System Organ Class and Preferred Term Safety Set
Table 14.3.5.3.1	Hematology Shift Table by Treatment at Interim Analysis Safety Set
Table 14.3.5.3.2	Laboratory Results: Hematology at Interim Analysis Safety Set
Table 14.3.5.4.1	Clinical Chemistry Shift Table by Treatment at Interim Analysis Safety Set
Table 14.3.5.4.2	Laboratory Results: Clinical Chemistry at Interim Analysis Safety Set
Table 14.3.6.2.1	Change from Baseline in Vital Signs at Interim Analysis Safety Set
Figure 14.3.6.2.1	Time-course plot of Vital Signs at Interim Analysis Safety Set
Table 14.3.7.1.1*	APACHE II Score at Interim Analysis Safety Set
Listing 16.3.1.1.2*	Deaths Safety Set

* Outputs were requested after the first DMC meeting.

References to ‘Interim Analysis’ will be removed from all titles and footnotes when outputs are provided at safety reviews.

Additional electronic reviews of AE listings provided by pharmacovigilance (PVG) will be conducted at planned time points and the DMC can request ad hoc reviews. See [Table 15-2](#) for a full summary of the planned reviews.

12. Changes in the Planned Analysis

As part of the primary efficacy analysis an additional analysis set PP Day 1-7 Part 1 has been added. The protocol states that primary endpoint should be carried out separately for Part 1 and Part 2, however to do this analysis on the PP Set, the PP Day 1-7 Part 1 Set is needed to be defined to obtain the analysis for Part 1 of the study.

The following are changes from the Protocol Amendment v2.0:

Table 12-1 Summary of Changes from Planned Analysis and Reason

Change	Change
List of subgroups (Sections 2.3 and 8)	Microbial Infection added
Secondary Efficacy Endpoints (Section 8.2)	Contrary to Section 7.7.2 of the protocol, two sets of outputs have not been produced for these endpoints. Instead, the planned summaries have been combined to present all four treatments for all patients (i.e., per the safety analysis).
Other Secondary Endpoints (Sections 3.2.3 and 8.2.2.1)	Kidney function at Days 14 and 21 will also assessed and analyzed.
Other Endpoints (Sections 3.2.4)	Total time in ICU/Intermediate care and Total time in hospital also based on time to decision of transfer.
Other Endpoints (Section 3.2.4)	Total time in ICU/Intermediate care and Total time in hospital, based on time to decision of transfer deleted.

13. Change History

Version (date)	Section	Summary of change
1.4 (06DEC2016)	2.3	FE Urea analysis added
1.4 (06DEC2016)	3.1	Schedule of events – treatment administration updated to be within 96 hrs from sepsis first diagnosis
1.4 (06DEC2016)	3.2.3	Added BUN/Urea clearance as other secondary endpoint
1.4 (06DEC2016)	3.2.3	Added kidney function assessment at Day 14, 21 and 28 as other secondary endpoint
1.4 (06DEC2016)	3.2.3	Added incidence of dialysis dependency at Day 60 and Day 90 as other secondary endpoint
1.4 (06DEC2016)	4	Added information on the assignment of patients to analysis sets who were recruited during the interim analysis
1.4 (06DEC2016)	4	Added information that all summaries will be provided by treatment arm
1.4 (06DEC2016)	4	Updated ‘average dose received’ and ‘received treatment group assignment’ categories
1.4 (06DEC2016)	4.3.2.2	ITT Part 1 Interim analysis set added
1.4 (06DEC2016)	4.3.2.2	PP Day 1 – 7 Part 1 analysis set added
1.4 (06DEC2016)	4.3.6	Iohexol analysis set added
1.4 (06DEC2016)	6.2	Acute physiology and chronic health evaluation (APACHE II) score added to baseline disease characteristics

Version (date)	Section	Summary of change
1.4 (06DEC2016)	6.2	Number and percentage of patients with vasopressor/inotropic therapy use added to baseline disease characteristics
1.4 (06DEC2016)	6.2	FE Urea added and creatinine clearance is using formula given in 8.1 section and CKD-EPI formula added in the appendix.
1.4 (06DEC2016)	8	Supportive analysis updated to include specific group categories as factors.
1.4 (06DEC2016)	8	Table added to provide an overall summary of the efficacy analyses
1.4 (06DEC2016)	8.1	Updated so only adjudicated Part 1 will be used in sensitivity analysis.
1.4 (06DEC2016)	8.1, 8.1.2	Adjudication committee review added for creatinine clearance data
1.4 (06DEC2016)	8.1, 8.1.2	Formula added for time-corrected endogenous creatinine clearance calculation
1.4 (06DEC2016)	8.1.4	Sensitivity analysis added to repeat primary endpoint analysis based on adjudicated Part 1 data. ANOVA analysis excluding any patients that died prior to Day 8 and descriptive statistics on the primary endpoint will be performed for the sensitivity analysis.
1.4 (06DEC2016)	8.2.2.1	Urine volume and urea clearance calculation formulas were added
1.4 (06DEC2016)	8.2.2.1	Details added on RRT-free day calculation method
1.4 (06DEC2016)	8.3	Added anti-drug antibody data as other efficacy endpoint
1.4 (06DEC2016)	8.3	Iohexol substudy details added
1.4 (06DEC2016)	8.1.5	Category for FE Urea added
1.4 (06DEC2016)	9.1.2	Separate summary of TEAEs where relationship to study drug is 'Possible', 'Probable' or 'Definite' removed
1.4 (06DEC2016)	9.2	Laboratory evaluations analyses modified to be based on shift tables as per normal ranges provided by the local laboratory
1.4 (06DEC2016)	11	Amended list of outputs provided for the interim analysis
1.4 (06DEC2016)	11	Added details of outputs provided for the DMC meetings
1.4 (06DEC2016)	Appendices 15.2, 15.3, 15.4	Added appendices of schedule of DMC reviews, weight ranges and pre-calculated corresponding volumes and CKD-EPI formula used for GFR calculation
2.0 (13JAN2017)	3.2	Total time in ICU/Intermediate care and Total time in hospital endpoint analysis based on time to decision of transfer deleted. Also both periods Day 1 to 28 and Day 1 to 90 added.
2.0 (13JAN2017)	4.3.3.1, 4.3.3.2, 4.3.3.2, 4.3.3.4	'Non-adherence to inclusion/exclusion criteria with enrollment of the patient' is used for eligibility criteria.
2.0 (13JAN2017)	8.1.1	Hyperlink for section 8.1.5 added.
2.0 (13JAN2017)	8.2.2.1	'Urine volume' replaced with 'Urine output' and the time course plot updated to be on urine output (ml/hr) and not on volume of urine

Version (date)	Section	Summary of change
2.0 (13JAN2017)	8.2.2.2	Sentence ‘non mechanical analysis’ replaced with ‘non mechanical ventilation’.
2.0 (13JAN2017)	8.3	Day 1-28 and the day1-90 for ICU discharge and hospital discharge used (like section 3.2).
3.0 (25SEP2017)	General	‘Time-corrected’ only used for reference to AUC of Creatinine Clearance. ‘Standardized’ used elsewhere.
3.0 (25SEP2017)	2.3 8.1.5	Added ≥ 24 hour category for Time from first diagnosis of SA-AKI to start of treatment
3.0 (25SEP2017)	3.2.4	Kaplan-Meier will be done once for time to discharge from ICU and time to discharge from Hospital (removed separate analyses for Days 1-28 and Days 1-90)
3.0 (25SEP2017)	4	Definition of baseline updated for subjects who were randomized but not treated
3.0 (25SEP2017)	4	Added text on handling of < or > for laboratory values and added Table 4-2 Serum Creatinine and CRP laboratory conversions
3.0 (25SEP2017)	4.3.3.4 5.1 8.2.1	Removed PP Day 1-28 Set and replaced with PP Day 1-7 Combined Set where appropriate
3.0 (25SEP2017)	6.1	Race category updated from ‘Not Applicable’ to ‘Not Collectable’.
3.0 (25SEP2017)	6.2	Local lab values for serum creatinine will be used if central lab values are not available.
3.0 (25SEP2017)	6.2	CKD-EPI formula will no longer be used if creatinine clearance values are not available.
3.0 (25SEP2017)	8.1	Added rule for standardized creatinine clearance calculation that when urine volume is <30ml/24 hour then standardized creatinine clearance will be set to 1ml/min.
3.0 (25SEP2017)	8.1.1	Clarification added that the p-values used in the equation for the combination test are 1-sided p-values.
3.0 (25SEP2017)	8.1.1	Time course plot for creatinine clearance will be repeated three times based on different selection based on imputation and adjudication of creatinine clearance data.
3.0 (25SEP2017)	8.1.2	Removed AUC from list of data reviewed by adjudication committee.
3.0 (25SEP2017)	8.1.5	All baseline variables of interest /subgroups will be used as additional covariates in the statistical models (not as by-groups). In addition, as a result, Baseline AKIN stages 2 and 3 will not be combined into an additional group.
3.0 (25SEP2017)	8.1.5	Updated categories for microbial infection and added rules for handling microbial infection data.
3.0 (25SEP2017)	8.1.5 8.2.2.3	GST-alpha measured using two separate kits. Quartiles will be calculated separately for the different kits
3.0 (25SEP2017)	8.1.5	Added clarification that subgroup summary tables will also be presented for ITT Part 1 Interim Set and ITT Part 2 Set
3.0 (25SEP2017)	8.2.1	For model convergence issues, site will be removed from the model and documented.

Version (date)	Section	Summary of change
3.0 (25SEP2017)	8.2.2.1	RRT: Removed exclusion of patients who died or withdrew from the study prior to Day 28 from the calculation of RRT-Free days. For the exploratory ANOVA, subjects who died before Day 28 whilst still on RRT will be assumed to have finished RRT on Day 28.
3.0 (25SEP2017)	8.2.2.1	Kidney Function: Reference eGFR will be using serum creatinine from eGFR only, Baseline Kidney Function will be assessed using creatinine clearance only. Days 14, 21 and 28 will be assessed using creatinine clearance if available or eGFR if not. LOCF will only be implemented for Days 60 and 90.
3.0 (25SEP2017)	8.2.2.2	Lung Function: Removed sentence stating PEEP and tidal volume will be assessed for invasive ventilation only. Added Table 8-2 Normal ranges for Lung Function parameters Added clarification that parameters are measured daily
3.0 (25SEP2017)	8.2.2.2	Mechanical Ventilation: Added +1 day to calculation for Time to being off ventilator.
3.0 (25SEP2017)	8.2.2.2	Deaths during 90 day study period: Added + 1 day to calculation for Time to death.
3.0 (25SEP2017)	8.2.2.2	Purine data: Section added
3.0 (25SEP2017)	8.3	Updated text for discharge from hospital for Day 1 to 28 and Day 1 to 90 and similarly for ICU. Added +1 day to calculation for Time to discharge from Hospital/ICU.
3.0 (25SEP2017)	8.3	Exogenous Creatinine Clearance section added
3.0 (25SEP2017)	9.1.6	Deaths during follow-up will be included in summaries and listings.
3.0 (25SEP2017)	9.2.2	Added normal ranges for pH.
3.0 (25SEP2107)	9.2.3	Corrected typo in 'performed'
3.0 (25SEP2017)	11	Reverted numbering back to original Interim analysis numbering
3.0 (25SEP2017)	14	Added references for lab conversions
3.1 (27 SEP2017)		27SEPT2017: Client sign off received on version 3.0 with request that two minor changes in wording were made as documented below. Client email confirmation received that they do not require client sign-off on version with minor changes.

Version (date)	Section	Summary of change
